18.3. RESPONSE CRITERIA

18.3.1. DOCUMENTATION OF NEW LESIONS

- The presence of a new lesion should be unequivocal: i.e. not attributable to differences in scanning technique, change in imaging modality or findings thought to represent something other than tumour (for example, some 'new' bone lesions may be simply healing or flare of pre-existing lesions).
- A lesion identified at a follow-up visit in an anatomical location that was not scanned at baseline is considered a new lesion and will indicate disease progression.

18.3.2. LESIONS THAT BECOME 'TOO SMALL TO MEASURE'

- If lesions or lymph nodes recorded as target lesions at baseline become too faint on CT scan to assign an exact measure, a default value of 5mm should be assigned. This default value is derived from the 5mm CT slice thickness
- If it is the opinion of the radiologist that the lesion has likely disappeared, the measurement should be recorded as 0mm.

18.4. EVALUATION OF TARGET LESIONS

Response criteria	Evaluation of target lesions
Complete Response (CR)	Disappearance of all target lesions (lymph nodes must be <10mm short axis)
Partial Response (PR)	At least 30% decrease in the sum of LD of target lesions, taking as reference the baseline sum of LD.
Progressive Disease (PD)	At least 20% increase in the sum of LD of target lesions, taking as reference the smallest sum LD recorded since the treatment started and at least 5mm absolute increase in this sum or the appearance of one or more new lesions.
Stable Disease (SD)	Neither sufficient shrinkage to qualify for PR nor sufficient increase to qualify for PD, taking as reference the smallest sum LD since the treatment started.

18.5. EVALUATION OF NON-TARGET LESIONS

Response criteria	Evaluation of non-target lesions
Complete Response (CR)	Disappearance of all non-target lesions
Incomplete response / Stable disease (SD)	Persistence of one or more non-target lesions
Progressive disease (PD)	Appearance of one or more new lesions and/or unequivocal progression of existing non-target lesions *

* To achieve 'unequivocal progression' on the basis of the non-target disease, there must be an overall level of substantial worsening in non-target disease such that, even in presence of SD or PR in target disease, the overall tumour burden has increased sufficiently to merit discontinuation of therapy. A modest 'increase' in the size of one or more non-target lesions is usually not sufficient to qualify for unequivocal progression status. Although a clear progression of a non-target lesion is exceptional, in such circumstances, the opinion of the treating physician should prevail and the progression status should be confirmed later on by the review panel (or Chief Investigator).

18.6. EVALUATION OF OVERALL RESPONSE

The table below provides a summary of the overall response calculation at each time point.

Target lesions	Non-Target lesions	New Lesions	Overall response
CR	CR	No	CR
CR	Incomplete response/SD	No	PR
CR	Not-evaluated*	No	PR
PR	Non-PD or not all evaluated	No	PR
SD	Non-PD or not all evaluated	No	SD
Not all evaluated	Non-PD	No	Not evaluable
PD	Any	Yes or No	PD
Any	PD	Yes or No	PD
Any	Any	Yes	PD

* When no imaging/measurement is done at all at a particular time point, the patient is not evaluable (NE) at that time point. If only a subset of lesion measurements are made at an assessment, usually the case is also considered NE at that time point, unless a convincing argument can be made that the contribution of the individual missing lesion(s) would not change the assigned time point response.

18.7. CONFIRMATION OF DISEASE PROGRESSION

For equivocal findings of progression (e.g. very small and uncertain new lesions; cystic changes or necrosis in existing lesions), treatment may continue until the next scheduled assessment. If at the next scheduled assessment, progression is confirmed, the date of progression should be the earlier date when progression was suspected.

Patients with a global deterioration of health status requiring discontinuation of treatment without objective evidence of disease progression at that time should be classified as having "symptomatic deterioration". Every effort should be made to document the objective progression even after discontinuation of treatment.

In some circumstances it may be difficult to distinguish residual disease from normal tissue. When the evaluation of complete response depends on this determination, it is recommended that the residual lesion be investigated (fine needle aspirate/biopsy) to confirm the complete response status.

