- Symptom assessment (NCI CTCAE v.4)
- Serum Thyroid Function Tests (Free T4 and TSH)
- Assessment of concomitant medications

NB. If the participant has any axitinib treatment interruptions \geq 1 week, please contact the trials office for advice on scheduling of subsequent follow up and research biopsy.

7.4. DAY 1 WEEK 5:

The following investigations should be conducted on day 1 of week 5 (+/- 72 hrs):

- Physical examination including ECOG performance status, body weight, temperature, blood pressure, heart rate, respiratory rate
- Haematology, coagulation, glucose, renal and liver function, serum calcium and LDH
- Urinalysis for protein
- Symptom assessment (NCI CTCAE v.4)
- Assessment of compliance with study medication
- Serum Thyroid Function Tests (Free T4 and TSH)
- Assessment of concomitant medications

NB. If the participant has any axitinib treatment interruptions \geq 1 week, please contact the trials office for advice on scheduling of subsequent follow up and research biopsy.

Dispense axitinib to patient (see section 8)

7.5. DAY 1 WEEK 8

Patient should be instructed to stop axitinib 5-7 days prior to biopsy (after 7 weeks of treatment)

NB. If the participant has any axitinib treatment interruptions \geq 1 week, please contact the trials office for advice on scheduling of subsequent follow up and research biopsy.

7.6. DAY 1 WEEK 9

The following investigations/assessments should be conducted on day 1 week 9 (+/- 72 hrs):

- Physical examination including ECOG performance status, body weight, temperature, blood pressure, heart rate, respiratory rate
- Haematology, coagulation, glucose, renal and liver function, serum calcium and LDH
- Urinalysis for protein
- Symptom assessment (NCI CTCAE v.4)
- Blood samples and urine sample for biomarker analysis (see Appendix B)
- CT thorax, abdomen and pelvis and assessment of response according to RECIST 1.1 criteria.
- Percutaneous biopsy of non-necrotic region of primary renal tumour (from same site as first biopsy if possible) via appropriate (US or CT) guidance (see Appendix B)
- Assessment of compliance with study medication (see section 8)
- Assessment of concomitant medications

Dispense axitinib, with instructions to patient to start 2-3 days after biopsy (see section 8)

NB: CT thorax, abdomen and pelvis should be carried out prior to biopsy

7.7. DAY 1 WEEK 13 (AND EVERY 4 WEEKS TO SIX YEARS/DISEASE PROGRESSION):

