7.8. PROCEDURE IF PATIENT IS WITHDRAWN FROM AXITINIB TREATMENT

- CT thorax, abdomen and pelvis and assessment of response according to RECIST 1.1 criteria prior to commencement of any subsequent treatment

7.9. PROCEDURE AT DISEASE PROGRESSION:

Axitinib therapy should be continued until there is clinically significant disease progression, after which treatment should be discontinued and the following investigations should be conducted.

- Physical examination including ECOG performance status, body weight, temperature, blood pressure, heart rate, respiratory rate
- Haematology, coagulation, glucose, renal and liver function, serum calcium and LDH
- Toxicity assessment (NCI CTCAE v.4)
- CT thorax, abdomen and pelvis and assessment of response according to RECIST 1.1 criteria prior to commencement of any subsequent treatment
- Blood samples and urine sample for biomarker analysis (see Appendix B)
- Biopsy of site of progression, or if not possible, percutaneous primary tumour biopsy via appropriate (US or CT) guidance (see Appendix B), one week after stopping axitinib treatment. Biopsy should be taken prior to commencement of any subsequent treatment.
- Assessment of concomitant medications

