7.11. FOLLOW UP

Patients should be followed up for survival and performance status every 12 weeks after treatment discontinuation.

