7.13. SCHEDULE OF ASSESSMENTS

Visit/Assessment	Up to 21 days Pre-registration	Pre-treatment day 1 week 1*	Day 1 week 3	Day 1 week 5	Day 1 Week 8	Day 1 week 9	Day 1 week 13	Day 1 week 17	Day 1 week 21	Day 1 week 25#	Disease progression
Confirmation of histological diagnosis of metastatic renal cell carcinoma	X										
Medical history	X										
Physical examination including ECOG performance status, body weight, height, temperature, blood pressure ⁷ , heart rate, respiratory rate	X	X	X	X		X	X	X	X	X	X
Haematology, coagulation, glucose, renal and liver function, serum calcium and LDH	X	X		X		X	X	X	X	X	X
Urinalysis for protein	X	X		X		X	X	X	X	X	
Symptom assessment (NCI CTCAE v.4)	X	X	X	X		X	X	X	X	X	X
Serum Thyroid Function Tests (Free T4 and TSH)	X		X	X			X ⁴		X		
Pregnancy test (serum or urine) if applicable	X										
CT thorax, abdomen and pelvis and tumour assessment using RECIST 1.1 criteria	X ¹					X		X		X ⁵	X
Percutaneous image guided biopsy of non-necrotic region of primary renal tumour and possibly one metastatic site (see Appendix B)	X ²					X					X ⁶
Blood samples and urine sample for biomarker analysis (Appendix B)		X				X					X
Assessment of compliance with study medication			X		X	X	X	X	X	X	
Dispense axitinib		X		X		X ³	X	X	X	X	
Stop axitinib 5-7 days prior to biopsy					X						
Assessment of concomitant medications	X	X	X	X		X	X	X	X	X	X

• * Day 1 week 1 assessments may be omitted if conducted within previous 7 days as part of pre-registration assessments (apart from pregnancy test)

• # Subsequent visits to take place 4 weekly thereafter to six years, after which they should take place 12 weekly.

1. CT thorax, abdomen and pelvis should be conducted prior to biopsy
2. One week prior to starting axitinib if possible.
3. Patient to restart axitinib 2-3 days after biopsy
4. Subsequent thyroid function tests should be conducted every 8 weeks to six years, after which they should be conducted 12 weekly
5. Subsequent tumour imaging to be performed 12 weekly thereafter and at treatment discontinuation/progression
6. Biopsy of site of progression, or if not possible, percutaneous image guided primary tumour biopsy. Biopsy should be taken prior to commencement of any subsequent treatment.

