8.4. DOSE INTERRUPTION AND REDUCTION

Patients experiencing non-haematological drug reactions greater than CTCAE Grade 2 or haematological reactions greater than CTCAE Grade 3 should undergo dose modification. The current version of the SmPC should be used to assess whether any adverse event is attributable to the drug.

Axitinib should be stopped in the event of significant toxicity and restarted if appropriate when toxicities have resolved. Recovery to acceptable levels of toxicity must occur within 4 weeks to allow recommencement of treatment.

Patients permanently removed from treatment for intolerable toxicity should receive a post treatment CT scan assessed according to RECIST 1.1 criteria, and should continue to be followed with regular tumour assessments until disease progression or start of new treatment, and for survival thereafter.

The criterion for dose modification for axitinib related adverse events is summarised in the table below:

8.4.1. CRITERIA FOR DOSE MODIFICATION FOR AXITINIB - RELATED ADVERSE EVENTS (OTHER THAN HYPERTENSION OR PROTEINURIA)

Related Adverse Events	INTERVENTION
Any Grade: Bleeding where medical intervention is required	Temporarily interrupt the axitinib dose.
Any Grade: Posterior reversible encephalopathy syndrome (PRES)	Patients with signs or symptoms should temporarily interrupt or permanently discontinue axitinib treatment. In case of severe or persistent arterial hypertension and symptoms suggestive of posterior reversible encephalopathy syndrome, a diagnostic brain magnetic resonance image (MRI) should be considered.
Moderate hepatic impairment (Child-Pugh class B)	A dose decrease is recommended
Grade 1 or 2	Continue at same dose level
Grade 3 non-haematologic treatment-related toxicity	Decrease dose to one lower dose level unless controlled with symptomatic medications.
Grade 3 asymptomatic biochemistry laboratory abnormalities	Continue at the same dose level at the discretion of the investigator
Grade 4 non-haematologic treatment-related toxicity or Grade 4 haematologic toxicity (other than those below)	Interrupt dosing; re-start at one lower dose level as soon as improvement to CTCAE Grade ≤2. If patient requires dose reduction below 2 mg BID, contact ICR-CTSU for discussion prior to implementation.
Grade 4 lymphopaenia or Grade 4 asymptomatic biochemistry laboratory abnormality	Continue at the same dose level at the discretion of the investigator

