10.2. ENDPOINT DEFINITIONS

10.2.1. PRIMARY ENDPOINT

The proportion of study participants alive and progression free at 6 months (day 1 week 25 visit). Progression will be measured from the date of study entry (registration date) until the first date of either death or confirmed progressive disease according to RECIST. Patients alive and free from progression will be censored at the date of last follow-up. The proportion of patients progression free at 6 months will be reported with 95% confidence interval. In addition, progression free survival will be presented using the Kaplan Meier product limit method with median progression free survival reported.

A blinded central review of CT scans will be conducted for verification purposes.

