10.3. INTERIM ANALYSIS AND DATA MONITORING

An Independent Data Monitoring Committee will meet approximately every 6 months to review accrual, safety and efficacy data. The subsequent replacement of patients who withdraw from treatment or who are unevaluable for reasons deemed not to be treatment related will be based on the advice of this committee. For completeness a sensitivity analysis of the progression free rate calculated by the Kaplan Meier product limit method will also be presented in which withdrawals are censored.

A formal interim analysis will be conducted once the first 37 patients have at least 6 months follow up data available. The principal analysis for publication will occur on the recommendation of the IDMSC and is expected once 99 patients have at least 6 months follow up data available (or have died).

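### Section 10.3 could let patients who stop for symptomatic deterioration be replaced in the fixed 11/37 and 32/99 counts, and 7.11 does not carry over the off-drug tumour imaging that 8.9 supports

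*Combined protocol and SAP*

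**What the plan says.** **Primary count.** Section 10.1 stops the trial if fewer than 11 of the first 37 patients are alive and progression free at 6 months. It declares worthwhile efficacy if at least 32 of the 99 entered are. Section 10.2.1 ties 6 months to the week 25 visit and runs the endpoint "until the first date of either death or confirmed progressive disease according to RECIST". Section 4.1 also specifies RECIST v1.1.

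**Symptomatic deterioration.** Section 18.7 defines a class of patients with "global deterioration of health status requiring discontinuation of treatment without objective evidence of disease progression at that time". It asks sites to try to document objective progression after the drug is stopped. It does not mention the primary count.

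**Replacement.** Section 10.3 leaves to the committee's advice the "replacement of patients who withdraw from treatment or who are unevaluable for reasons deemed not to be treatment related". It adds a Kaplan-Meier sensitivity analysis that censors withdrawals.

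**Imaging after stopping.** The texts differ:
- 7.8 requires one CT at withdrawal from axitinib, with "assessment of response according to RECIST 1.1 criteria prior to commencement of any subsequent treatment".
- 7.11, the paragraph on follow-up after stopping, says: "Patients should be followed up for survival and performance status every 12 weeks after treatment discontinuation". It names no CT.
- 8.4 covers patients removed for toxicity, who "should continue to be followed with regular tumour assessments until disease progression or start of new treatment".
- 8.9 covers every discontinuation. It requires follow-up for progression and then survival, and refers to the Schedule of Assessments.
- 7.13 has CT columns at weeks 9, 17 and 25. Its footnote 5 reads: "Subsequent tumour imaging to be performed 12 weekly thereafter and at treatment discontinuation/progression".
- The 7.7 heading runs visits "EVERY 4 WEEKS TO SIX YEARS/DISEASE PROGRESSION".

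**Missing scans.** Section 18.6 makes a patient with no imaging at a time point not evaluable at that time point.

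**The concern.** The efficacy decision is a fixed count, so one or two patients can settle a borderline result. Section 1.6 calls this a very poor prognosis group and 18.7 foresees stops for deterioration, so such patients are to be expected.

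Many will fail by a written route: death, PD on the CT at discontinuation, PD on a later scan, or non-target progression as judged under 18.5. Two openings remain for the others.

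1. **Replacement.** Deterioration from the cancer can be called not treatment related. Section 10.3 would then allow the committee to advise replacing a patient who is likely to fail before the week 25 outcome is known.
2. **Missed progression.** A site that works from 7.11 may do no CT after the one at discontinuation. If that CT shows no PD and the patient is alive at week 25, 10.2.1 would count the patient as progression free even if the disease had progressed unseen.

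The trial is open label with a single arm, so both matters are better settled before outcomes are known.

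**Working it through.** **Inputs from section 10.1:** n1 = 37, continue if X1 ≥ 11; n2 = 62, N = 99, success if X ≥ 32; p0 = 0.25, p1 = 0.40; one-sided alpha 0.05, power 90%.

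**Assumed input:** k = 1 or 2 of 99 patients stop for deterioration without RECIST PD and are alive at week 25. The documents give no rate.

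**Formula.** P(success | p) = Σ over x = 11 to 37 of Bin(x; 37, p) × P(Bin(62, p) ≥ 32 − x).

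**Step 1: the plan's own figures.**
- p = 0.25: 0.0493, within the stated 0.05.
- p = 0.40: 0.9002, matching the stated 90%.

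The design reproduces and is not in question.

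**Step 2: handling of the k patients at the null rate.** Each case changes the success probability p that enters the formula.

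| Case | p | k = 1 | k = 2 |
|---|---|---|---|
| A. They are failures and are replaced | 0.25/(1 − k/99) = 0.2526; 0.2552 | 5.6% | 6.3% |
| B. The 25% treats them as failures, but they are counted as successes | 0.25 + k/99 = 0.2601; 0.2702 | 7.8% | 11.6% |
| C. The 25% is RECIST-defined and they are counted by RECIST | 0.25 | 4.9% | 4.9% |
| D. The 25% is RECIST-defined, they are RECIST successes, and they are replaced | (0.25 − k/99)/(1 − k/99) = 0.2423; 0.2345 | 3.4% | 2.2% |

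Cases A and D are both replacement and move the error in opposite directions. What matters is the status the patient would have had at week 25, which is unknown if replacement is decided earlier.

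**Step 3: power at 40%.**
- Case D: p = (0.40 − k/99)/(1 − k/99) = 0.3939 or 0.3876, giving 88.2% or 86.0%.
- A stricter count with the k patients as failures, if the 40% was meant to include them as successes: p = 0.40 − k/99 = 0.3899 or 0.3798, giving 86.8% or 82.9%.

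**Step 4: the follow-up texts side by side.** Section 8.9 covers all discontinuations, requires follow-up for progression and points to the schedule. The CT columns in 7.13 are calendar weeks, and nothing there ends them when the drug stops. Section 18.7 asks for progression to be documented after stopping. These support CTs off drug. Section 7.11 omits them, and only 8.4, for toxicity stops, spells out regular tumour assessments off drug. The intention is fairly clear, but the paragraph a site would consult after stopping does not state it.

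**Step 5: the existing sensitivity analysis.** The one in 10.3 censors withdrawals. It never counts them as failures, so it does not test the unfavourable reading.

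**The case against.** The strongest reply is that a rule already exists. Sections 4.1 and 10.2.1 define events as death or RECIST progression, so a living patient scanned without PD is progression free. That stands, and the primary definition needs no change. A reader might infer that these patients have no status at all in the primary count. The documents do not support that for a scanned patient. It is less settled for a patient with no week 25 scan, whom 18.6 makes not evaluable at that time point.

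Second, imaging off drug is already supported by 8.9, 18.7 and the 7.13 columns. This also stands. A reader of 7.11 alone might infer that the plan stops CTs at discontinuation; taken as a whole, it does not. What is left is a conflict of wording, although one that bears on the primary endpoint.

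Third, replacement is not automatic. It needs the committee's advice and a reason deemed not treatment related, and 10.1 speaks of the 99 entered. That limits the risk, but nothing in 10.3 excludes patients stopped for deterioration.

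Fourth, a reader might infer that every open reading favours axitinib. Case D shows otherwise: replacing a RECIST success lowers the chance of passing. The 11.6% also needs a 25% null rate that treats these patients as failures, whereas the protocol's only stated progression definition is RECIST.

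**Conclusion.** The point holds in a limited form and is minor. As worded, 10.3 can allow patients who stop for symptomatic deterioration or clinical progression to be replaced before their week 25 outcome is known. Section 7.11 is out of line with 8.9, so progression before week 25 can be missed at a site that follows it.

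For an assumed 1 or 2 such patients of 99, the type I error runs from 2.2% to 11.6% against the design's 4.9%. Replacing failures gives 5.6% or 6.3%. The upper values, 7.8% and 11.6%, apply only if the 25% null treats these patients as failures. If it is RECIST-defined, counting them by RECIST causes no inflation. The direction of bias is not established. The sample-size calculation is correct.

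**What to change.** (a) **Section 10.3:** state that patients stopped for symptomatic deterioration or clinical progression remain among the 37 and the 99 and are not replaced.

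(b) **Section 7.11, with a footnote in 7.13:** align with 8.9 and extend the 8.4 wording to all stops. Anyone who stops without RECIST PD keeps the scheduled week 9, 17 and 25 CTs until PD, death or new systemic therapy.

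(c) **Section 10.2.1:** keep the RECIST-only primary definition, which blinded central review can verify. Add a sensitivity count against 32/99 in which patients with symptomatic deterioration, new therapy before week 25 or no evaluable week 25 scan are failures. This covers patients whose CTs end under (b) because new therapy has begun.

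**Cost:** a few sentences, one extra analysis, and at most two or three CTs each for a small number of patients. The real downside is asking deteriorating patients to attend for scans. The RECIST-only decision rule is unchanged; the sensitivity count is stricter, as step 3 of the working shows.

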18.8. DURATION OF OVERALL RESPONSE

The duration of overall response is measured from the time measurement criteria are met for CR or PR (whichever status is recorded first) until the first date that recurrence or PD is objectively documented, taking as reference for PD the smallest measurements recorded since the treatment started.

